3.2 Statistical calculations

Categorical variables will be compared using χ^2 test or the Fisher exact test whereas continuous variables will be assessed using either paired test or Wilcoxon signed rank test after checking for normal distribution. Analyses will be performed with SPSS software (SPSS, Inc., Chicago, IL) and $p < 0.05$ will be considered a significant difference between high-dose statin therapy and evolocumab plus high-dose statin therapy.

[figure not shown]
No prior data is available regarding direct antiplatelet effects of evolocumab. Sample size calculation is mainly based on our previous experience in pharmacodynamic studies. In this study, 50 patients are needed to detect the absolute difference of 14% (~20% relative difference) in ADP-induced aggregation after evolocumab plus high dose statins compared to previous high dose statin therapy alone in these same patients with a power of 91%, a two sided alpha = 0.05 and SD of 30%. Assuming a 16% drop out rate, we need 60 patients in total. Calculations based on a paired t-test.

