1.2 Hypothesis

Treatment with evolocumab plus high-dose statin is associated with a reduction in platelet activation and aggregation and biomarkers associated with platelet activation, oxidative stress, and inflammation.

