Relative difference = 100 * (baseline on high dose statin value – post high dose statin plus evolocumab value) / baseline on high dose statin value

3.1.1 **Secondary Endpoints**

- Relative differences in AA- and collagen-induced platelet aggregation between high dose statin therapy and evolocumab plus high-dose statin therapy.

- Relative differences in platelet bound p-selectin, oxLDL, soluble LOX-1 receptor, between high dose statin therapy and evolocumab plus high-dose statin therapy.
- Relative differences in lipid profile, oxLDL, soluble LOX-1 receptor, fibrinogen, hsCRP, p-selectin, atherox (soluble markers) between high dose statin therapy and evolocumab plus high-dose statin therapy.
- Relative differences in platelet-fibrin clot characteristics and shear-induced platelet aggregation between high dose statin therapy and evolocumab and high-dose statin therapy
- Relative differences in ABI between high dose statin therapy. and evolocumab and high-dose statin therapy
- Relative differences in urinary 11-dh-thromboxane B2 levels between high dose statin therapy and evolocumab plus high-dose statin therapy.
- Relative differences in urinary 8-iso-Prostaglandin F2 α levels between high dose statin therapy and evolocumab plus high-dose statin therapy.

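### Section 3.2 calls any p < 0.05 significant, without limiting this to the primary endpoint, although 3.1.1 lists about 13 to 18 unranked non-lipid secondary measures

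*Combined protocol and SAP*

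**What the plan says.** Section 3.2 of the combined protocol and SAP gives one testing rule. It says that "continuous variables will be assessed using either paired test or Wilcoxon signed rank test after checking for normal distribution", and that p < 0.05 "will be considered a significant difference between high-dose statin therapy and evolocumab plus high-dose statin therapy". The synopsis repeats the 0.05 threshold. Neither place restricts it to the primary endpoint.

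The primary endpoint in 3.1 is the relative difference in maximal ADP-induced aggregation. The sample size in 3.2 rests on that alone: "50 patients are needed to detect the absolute difference of 14% (~20% relative difference) in ADP-induced aggregation".

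Section 3.1.1 then lists seven bullets of secondary endpoints, most holding several measures. One of them reads "Relative differences in lipid profile, oxLDL, soluble LOX-1 receptor, fibrinogen, hsCRP, p-selectin, atherox (soluble markers".

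Section 1.2 states the hypothesis as a "reduction in platelet activation and aggregation and biomarkers associated with platelet activation, oxidative stress, and inflammation". It does not say how many measures must move, or which.

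The documents contain no multiplicity adjustment, no order of testing, no false-discovery control and no statement that secondary p-values are descriptive. Platelet-fibrin clot characteristics and shear-induced aggregation are exploratory in the synopsis but secondary in 3.1.1.

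**The concern.** A reader who sees a result called significant at 0.05 takes the risk of a chance finding to be 5%. That holds for one prespecified test. It does not hold for the best of a dozen or more tests that all carry the same label.

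This matters here because the hypothesis spans platelet activation, aggregation, oxidative stress and inflammation. One marker that falls at p < 0.05 could be presented as support for it even if ADP-induced aggregation does not change. The primary objective in the synopsis makes this easier. It names platelet activation as well as aggregation, while the primary endpoint covers only ADP-induced aggregation. Section 3.2 also says that no earlier data exist on a direct antiplatelet effect of evolocumab, so an isolated p < 0.05 would have little prior support.

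**Working it through.** **1. The plan's own figure.** Inputs from 3.2: difference 14%, SD 30%, n = 50, two-sided alpha 0.05, paired t-test.

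- Standardised shift: (14/30) × √50 = 3.30.
- Power, normal approximation: Φ(3.30 − 1.96) = 91.0%. With the noncentral t it is 89.9%. The stated 91% is reproduced.
- Dropout: 50/0.84 = 59.5, so 60 patients, as stated.

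This sizing is for one test at 0.05. The documents give no error rate for the secondary set.

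**2. Counting the non-lipid secondary measures** (3.1.1, with the clot measures as itemised in 1.1):

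| Group | Tests |
|---|---|
| AA- and collagen-induced aggregation | 2 |
| Platelet-bound bullet: p-selectin, oxLDL, LOX-1 | 3 |
| Soluble markers: oxLDL, LOX-1, fibrinogen, hsCRP, p-selectin, Atherox | 6 |
| Clot characteristics by TEG6S | 3 |
| Shear-induced aggregation | 1 |
| ABI | 1 |
| Urinary 11-dh-TxB2 and 8-iso-PGF2α | 2 |
| **Total** | **18** |

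Dropping the clot and shear measures, which the synopsis calls exploratory, gives 18 − 4 = 14. The LOX-1 entry in the platelet-bound bullet is worded as the soluble receptor and may repeat the plasma marker. Counting it once gives 13. The lipid profile is left out because section 1.3 expects a strong LDL reduction, so those tests are not true nulls.

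**3. Chance of at least one p < 0.05 in either direction, if none of the measures changes.** With m independent tests at one visit this is 1 − 0.95^m.

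- m = 13: 1 − 0.513 = 48.7%
- m = 14: 51.2%
- m = 18: 1 − 0.397 = 60.3%

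The expected number of false positives is 0.05m: 0.65 for 13 tests and 0.90 for 18.

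**4. Chance of at least one hit in the supporting direction.** The hypothesis is directional, and under the null half of the two-sided hits go the other way. Each test therefore contributes 2.5%, and the chance is 1 − 0.975^m.

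- m = 13: 1 − 0.720 = 28.0%
- m = 18: 1 − 0.634 = 36.6%

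**5. Correlation.** The documents give no correlations between markers. As an assumption, take normal test statistics with a common correlation ρ, aligned so that favourable changes go together.

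| Tests | ρ | Either direction | Supporting direction |
|---|---|---|---|
| 13 | 0 | 49% | 28% |
| 13 | 0.3 | 42% | 21% |
| 13 | 0.5 | 33% | 17% |
| 18 | 0 | 60% | 37% |
| 18 | 0.3 | 51% | 26% |
| 18 | 0.5 | 40% | 20% |

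**6. Cost of a formal adjustment.** The first Holm step across 18 tests is 0.05/18 = 0.0028. For a marker with the planning effect (14/30, n = 50), power by the noncentral t falls from 90% at 0.05 to 56% at 0.0028.

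**The case against.** The strongest reply is that this is a small, single-arm pharmacodynamic study with no clinical endpoints. It has one primary endpoint, is sized on that endpoint, and states no confirmatory secondary claim. Secondary tests do not touch the primary alpha. All of this stands. It limits the point to how secondary p-values are labelled and read, and it argues against a mandatory adjustment.

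The counts are also open to argument. ABI is not plainly a platelet, oxidative-stress or inflammation marker. The oxLDL measures may not be clean nulls, since section 1.3 links high LDL to the formation of oxLDL. Starting from 13 tests, leaving out ABI gives 12 (46%), leaving out the two oxLDL measures instead gives 11 (43%), and leaving out both gives 10 (40%), under independence and in either direction. So whether the chance exceeds one half depends on counting choices. That it is far above 5% does not.

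Three stronger readings are tempting, and the documents do not support them.

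- A reader might count about 22 tests by adding four lipid components. The documents do not list the components, and a lipid effect is expected.
- A reader might infer that the trial will probably produce a false finding in favour of the hypothesis. In the supporting direction the chance is 37% at most for 18 tests at one visit. Independence is also doubtful, because all measures come from the same patients and oxLDL and p-selectin each appear both on platelets and in plasma.
- A reader might add the 15 measures also sampled at 24 hours, for 33 tests and 1 − 0.95^33 = 82%. Section 3.1.1 does not say that this visit is tested. Changes at the two visits would also share the same statin-alone value, so they cannot be independent.

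**Conclusion.** The point holds as a matter of labelling and interpretation. Followed as written, 3.2 lets any of about 13 to 18 non-lipid secondary measures be called significant at 0.05. If none of them changes, the chance of at least one such result at a single visit is about 49–60% under independence and about 33–40% at correlation 0.5. In the direction of the hypothesis it is about 28–37% and 17–20%.

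These figures assume that all counted measures are true nulls, that one visit is tested, that each test has its nominal 5% error rate, and that correlation is common to all pairs where it is used. The lowest of them is still more than three times 5% (or nearly seven times the 2.5% that one test carries in the supporting direction). The primary endpoint's error rate is unaffected, and the documents do not show that a false supportive finding is more likely than not.

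**What to change.** In 3.2, and in the matching synopsis sentence:

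- Reserve the word significant at p < 0.05 for the primary endpoint.
- Report every secondary and exploratory measure as an estimate with a 95% confidence interval and a p-value labelled nominal.
- State that these results do not by themselves establish the hypothesis in 1.2.
- Give the clot and shear measures the same tier in the synopsis and in 3.1.1.

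Holm across the non-lipid secondary measures is optional. It is worth its loss of power only if the sponsor wants a confirmatory secondary claim. In that case the set of measures and the visit should be fixed in advance.

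The cost is a few sentences, with no extra patients, samples or visits. The downside is that single secondary markers can no longer be called significant.

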3.3 Clinical endpoints – None

4.0 EVolocumab

Two doses of evolocumab will be administered in this trial, given 4 weeks apart (see visit schedule). Each evolocumab dose to be administered is 420mg. The dosage form and strength of evolocumab supplied for this trial is 140mg/mL solution in a single-use prefilled SureClick autoinjector. To administer 420 mg of evolocumab, three separate subcutaneous injections, given consecutively within 30 minutes will be administered to subjects. Evolocumab will be administered by a qualified member of the study staff.

Figure 3 Guide to Parts

4.1 Study Treatment Administration

Study treatment will be maintained, stored, and distributed by the research pharmacy. Once the evolocumab is available for administration from the pharmacy, follow the following steps:

Step 1: Prepare

Step 1A: Prepare 3 prefilled autoinjectors for administration. Wait 30 minutes for the autoinjectors to reach room temperature before injecting. Do not heat autoinjectors.

Step 1B: Inspect all SureClick autoinjectors. Check the expiration dates.

Step 1C: Gather all materials needed for the injection and wash hands well with soap and water.

Step 1D: Prepare and clean an injection site. Body areas that can be used include: thigh; abdomen, except for 2-inch area around the navel; and outer area of upper arm. *For the second and third injections, use a different spot than the last injection.* Do not inject into areas where the skin is tender, bruised, red, or hard.

Step 2: Get ready

Step 2A: Pull the orange cap off only when ready to inject. Do not leave the orange cap off for more than five minutes. This can dry out the study drug.

Step 2B: Stretch or pinch the injection site to create a firm surface.

Step 3: Inject

Step 3A: Hold the stretched or pinched skin. With the orange cap off, place the yellow end of the autoinjector on the skin at 90 degrees. Do not touch the gray start button yet.

Step 3B: Firmly push down the autoinjector onto the skin until it stops moving. *You must push all the way down but do not touch the gray start button until ready to inject.*

Step 3C: When ready to inject, press the gray start button. You will hear a click.

Step 3D: Keep pushing the autoinjector down on the skin. Then lift thumb while still holding the autoinjector on skin. Each injection could take about 15 seconds. The medicine window will turn from clear to yellow when the injection is done. You may hear a second click.

Step 4: Finish

Step 4A: When the injection is done, throw away the used autoinjector and orange needle cap.

Step 4B: Check the injection site. If there is blood, press a cotton ball or gauze pad on the injection site. Apply adhesive bandage if needed. *Do not rub the injection site.*

Repeat steps 1B to 4B for the second and third injections. Total dose administered should be 420 mg. Use a different injection site for each injection. Administer injections consecutively within 30 minutes.

4.1 Evolocumab storage

The evolocumab prefilled SureClick autoinjectors are stored in the original carton and are kept in refrigerated storage. Allowed temperature excursions while in storage is 36°F to 46°F (2°C to 8°C). Once removed from the refrigerator, the autoinjectors should be kept at room

temperature at 68°F to 77°F (20°C to 25°C) in the original carton and must be used within 30 days. The prefilled autoinjectors cannot be frozen. Do not use a prefilled autoinjector that has been frozen.

5 DATA MANAGEMENT

5.1 Data collection

Designated study site staff will record data required by the protocol into the case report forms (CRFs) and enter it into the electronic database. Authorized research staff will review the CRFs for completeness and accuracy and make any necessary corrections to the data entered into the electronic database.

5.2 Confidentiality, data storage, and retention

Information about study subjects will be kept confidential and managed according to the requirements of the Health Insurance Portability and Accountability Act of 1996 (HIPAA). Each subject screened and enrolled will be assigned a subject identification number (ID) and a list of subjects with their corresponding subject ID will be maintained separately from collected data.

Physical CRFs will be stored in the research site in a locked office and electronic subject data will be locked in a password protected file on a secure internet server, accessed only by authorized research staff. All data records will be stored on site until 2 years after the investigation is formally discontinued. Paper records will be shredded and recycled.

6 VISIT SCHEDULE AND ASSESSMENTS

Informed consent will be obtained from subjects meeting the inclusion criteria and none of the exclusion criteria before the initiation of any study-specific procedures. The study comprises of 2 periods: (1) high-dose (HD) statin therapy and (2) HD statin + evolocumab therapy. Subjects will be on a HD statin therapy for 8 weeks followed by the initiation of evolocumab 420mg Q 4 weeks x 2 doses, in addition to HD statin therapy for another 8 weeks. Required assessments for each study visit are listed in Table 1. Subjects should be seen for all visits on the designated day or according to the allowed window period (see Table 1).

The study requires 5 clinic visits. Each clinic visit (except visit 4) includes laboratory measurements, safety assessment, and health and concomitant medication review. A complete physical exam and safety laboratory assessment are required for visits 1 and 2.

6.1 Laboratory measurements

Laboratory measurements (see section 2.2) will be obtained at baseline (prior to study-recorded/initiated 8 week HD statin therapy), end of 8 weeks HD statin therapy, 24 hours after first evolocumab (420mg Q 4 weeks) dose, and at end of study (after 8 weeks of HD statin + evolocumab therapy). The study will require clinic visits during the required laboratory measurements.

6.2 Health and concomitant medication review

During the follow-up clinic visits, changes in participant's medical condition (any new diagnosis, scheduled surgical procedures, etc) and concomitant medications should be updated. Eligibility will be re-confirmed, adverse events reported, side effects and symptoms assessed.

6.3 Physical Exams

A physical exam will be conducted by the investigator or research nurse during the screening period after obtaining consent to evaluate the general status of the subject and to further elucidate patient symptoms, risk factors, or concerns that may increase the subject's risk for adverse reactions to the study treatment. A physical evaluation may be conducted as a nursing assessment if a physical exam was performed as standard of care ≤ 1 month prior to screening or at visit 2 if no AE/SAE's have occurred.

6.4 Safety assessments

Safety assessments will consist of monitoring and recording of adverse events and serious adverse events (see section 8). The occurrence of adverse events should be sought by non-directive questioning of the subject at each visit during the study. AEs may also be detected when these are volunteered by the subject during or between visits or through physical examination, laboratory test, or other assessments. Medical conditions/diseases present before starting the study drug are considered AEs only if they worsen after starting the study drug. Abnormal laboratory values or test results constitute AEs only if they induce clinical signs or symptoms, are considered clinically significant, or require therapy. Abnormal values that constitute a SAE or lead to discontinuation of administration of study drug must be reported and recorded as an AE. Adverse event collection will commence after screening and initiation of the HD statin.

Additional assessments required to ensure safety of subjects should be administered as deemed necessary by the investigator on a case by case basis.

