1.3 Background and Significance

Peripheral arterial disease affects about 8.5 million Americans aged ≥ 40 years. PAD is the third leading cause of atherosclerotic vascular morbidity after coronary heart disease and stroke.^{1,2} PAD is a manifestation of diffuse systemic atherosclerosis that coexists with coronary artery and cerebroarterial disease. Patients with PAD often have a very large atherosclerotic burden and large atherosclerotic burden has been associated with heightened platelet reactivity measured in systemic circulation.⁸ About 10–20% of people with PAD have intermittent claudication, another 50% have atypical leg symptoms, and those without exertional leg pain have poor mobility compared with individuals without peripheral symptoms. Patients with PAD have roughly a three-fold increase in risk of mortality compared with those without peripheral artery disease.² Ankle-brachial index (ABI) measurement is a well-established tool, to identify PAD.

With the expanding size of the elderly population, PAD is similarly a major growing clinical problem with limited current therapeutic options. Patients with PAD primarily die from thrombotic events - heart attack and stroke. The current antithrombotic agents administered for prophylaxis are aspirin and clopidogrel.⁹ High LDL is a major risk factor for PAD and therefore lipid-lowering therapy constitutes another important therapeutic intervention for patients with PAD. Statin therapy has been shown to improve walking performance, resting and post-exercise ABI and claudication.³ In addition, higher statin doses and lower LDL-cholesterol levels have been shown to be independently associated with improved outcomes in PAD patients.⁴ The latter finding indicates that significantly lower LDL-cholesterol may be associated with better clinical outcomes and supports proprotein convertase subtilisin/kexin type 9 (PCSK9) antibody therapy in patients with PAD.

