- Subject has received drugs via a systemic route that have known major interactions with background statin therapy within 1 month before randomization or is likely to require such treatment during the study period (e.g. cyclosporine, clarithromycin, HIV protease inhibitors, gemfibrozil)
- Female subject who is unwilling to use at least 2 effective birth control methods for at least 1 month before screening and 15 weeks after the end of treatment with investigational products, unless the subject is sterilized or postmenopausal
- Subject is pregnant or breast feeding, or planning to become pregnant or to breastfeed during receipt of investigational products and within 15 weeks after the end of study treatment
- Known previous hypersensitivity reaction/s to the investigational products' active components and excipients
- Subjects treated with any anticoagulant
- Patients treated with Prasugrel or Ticagrelor
- Subject likely to not be available to complete all protocol-required study visits or procedures, to the best of the subject's and investigator's knowledge
- History or evidence of any other clinically significant disorder, condition, or disease other than those outlined above that, in the opinion of the investigator, may compromise the ability of the subject to give written informed consent, would pose a risk to subject safety or interfere with the study evaluation, procedures, or completion

** Acceptable methods of contraception (birth control) while taking part in this study are:*

- *Total Abstinence (no sexual intercourse), absence of menstrual periods in women for more than one year after menopause (change of life), sterilization surgery, including tubal ligation (tubes tied) or hysterectomy (removal of the uterus or womb) in women or a vasectomy in men.*
- *Oral contraceptives (birth control pills), intrauterine device (IUD), implantable or injectable contraceptives (Norplant or Depo-Provera), contraceptive patch, vaginal ring or use of condom with spermicide. These methods must be used exactly as directed.*

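### Bleeding is neither prespecified nor directly asked about in a trial that seeks an antiplatelet effect, and sections 8.4 and 8.5 disagree on whether a minor bleed would be recorded

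*Combined protocol and SAP*

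**What the plan says.** **Aim.** The hypothesis in section 1.2 is that "Treatment with evolocumab plus high-dose statin is associated with a reduction in platelet activation and aggregation". Section 3.2 sizes the trial on the primary endpoint: "50 patients are needed to detect the absolute difference of 14% (~20% relative difference) in ADP-induced aggregation".

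**Background therapy.** Section 1.3 says of PAD in general: "The current antithrombotic agents administered for prophylaxis are aspirin and clopidogrel". The exclusions in section 2.1.1 include "Subjects treated with any anticoagulant" and "Patients treated with Prasugrel or Ticagrelor". Aspirin and clopidogrel are neither excluded nor required.

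**How adverse events are sought.** Section 6.4 prescribes: "The occurrence of adverse events should be sought by non-directive questioning of the subject at each visit during the study". It then adds: "AEs may also be detected when these are volunteered by the subject during or between visits or through physical examination, laboratory test, or other assessments". Section 6.2 has side effects and symptoms assessed at follow-up visits, section 6.6 covers counselling on side effects and when to call, and Table 1 marks adverse events at all five visits.

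**What is recorded.** Section 8.4 puts on the CRF all SAEs and those non-serious events that lead to permanent discontinuation, and says other non-serious events are not collected. Section 8.5 requires adverse events from the start of study medication to the last day of participation to go on the AE CRF, without that restriction.

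**Endpoints.** Section 3.3 reads "Clinical endpoints – None".

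**The concern.** If the drug does reduce platelet aggregation, the obvious clinical counterpart is bleeding, above all in patients already on an antiplatelet agent. That link is an inference from mechanism; the documents state no bleeding hypothesis. Bruising, nosebleeds and gum bleeding are easily left unmentioned when nobody asks about them, and under section 8.4 they would not be collected even if mentioned.

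What is at stake is how a positive result is read. The report could claim an added antiplatelet effect and show few or no non-serious bleeds, and a reader could take that as reassurance when the method was not set up to find them. In a single-arm study the statin-only period is the only internal comparator, and the two periods are not questioned equally.

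**Working it through.** **1. The plan's own figure.** The only design calculation is the sample size in section 3.2: difference 14, SD 30 (taken as the SD of the within-patient difference), two-sided alpha 0.05, n = 50.
- Normal approximation: power = Φ(14/30 × √50 − 1.96) = Φ(3.30 − 1.96) = 0.910, which matches the stated 91%. The exact paired t gives 0.899.
- Dropout: 50/(1 − 0.16) = 59.5, so 60, which matches.

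The figure reproduces. It bears on this point only by supplying n = 50 completers.

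**2. Each detection route, tested against non-serious bleeding on evolocumab.**

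| Route | Where | Does it target bleeding? |
|---|---|---|
| Non-directive questioning | 6.4 | No, by design |
| Volunteered reports | 6.4 | Only if the patient raises it |
| Symptom review | 6.2 | Bleeding not named |
| Physical exam | 6, 6.3, Table 1 | V1 and V2 only. V2 is the day of the first dose, and section 7.2 lists the exam before the injection, so no scheduled exam follows a dose |
| Safety laboratory tests | 2.2.1, Table 1 | CMP and CK; no haemoglobin or blood count listed |
| Endpoints | 3.1, 3.3 | No bleeding measure |

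**3. Recording.** For a minor bleed that is reported and does not lead to discontinuation, section 8.4 says it is not collected and section 8.5 says it goes on the AE CRF. Both cannot apply. Elicitation is a separate step: even if section 8.5 prevails, a bleed that nobody learns of is not recorded.

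**4. Balance between periods.** Adverse event collection starts after statin initiation (6.4). The 8 statin-only weeks are therefore covered by one questioning (V2), and the 8 evolocumab weeks by three (V3, V4, V5), of which V3 comes only 24 hours after the first dose.

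**5. Illustration, with assumed rates.** The documents give neither a true bleeding rate p nor a capture fraction s. With 50 completers, and supposing every captured event is recorded, P(no bleed recorded) = (1 − p·s)^50:

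| Assumed p | s = 10% | s = 25% | s = 50% | s = 100% |
|---|---|---|---|---|
| 5% | 0.78 | 0.53 | 0.28 | 0.08 |
| 10% | 0.61 | 0.28 | 0.08 | 0.005 |
| 20% | 0.36 | 0.08 | 0.005 | <0.001 |

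For example, 0.20 × 0.10 = 0.02 and 0.98^50 = 0.364; 0.20 × 0.25 = 0.05 and 0.95^50 = 0.077. A result of 0/50 would carry an exact two-sided 95% upper limit of 1 − 0.025^(1/50) = 7.1%, which describes recorded bleeding, not bleeding that occurred. If section 8.4 is applied literally, s is 0 for non-serious, non-discontinuing bleeds whatever the questioning, and none is recorded.

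**The case against.** The strongest case against is that this is a short pharmacodynamic study whose lack of clinical endpoints is an explicit choice, that section 3.2 says no prior data exist on direct antiplatelet effects of evolocumab, and that open versus prompted questioning is a recognised trade-off in which prompting brings in more minor events. The patients at higher bleeding risk from anticoagulants, prasugrel or ticagrelor are already excluded. All of this stands, and it makes the point an improvement rather than an error.

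Several stronger readings are tempting, and the documents do not support them:
- *Events are sought solely by non-directive questioning.* Sections 6.2 and 6.4 provide other routes. What can be said is that none is directed at bleeding.
- *The drug is tested on top of aspirin or clopidogrel.* Both are permitted and described as usual care; neither is required, and no proportion of users is given.
- *The trial will yield no usable bleeding information.* Serious bleeds, including medically significant ones (8.2), and bleeds that lead to permanent discontinuation are captured under either recording rule.
- *The under-count has a known size.* It follows wholly from the assumed p and s. At p = 20%, raising capture from 10% to 50% cuts the chance of recording none from 36% to 0.5%.

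The unequal questioning also cuts the other way: more questioning on evolocumab would tend to raise counts in that period. It is a reason not to compare unprompted counts between periods, not evidence of an under-count on evolocumab.

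One could also hold that the conflict between sections 8.4 and 8.5 is the whole problem. It is the most demonstrable part, but settling it in favour of full recording would still leave bleeding unasked about.

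**Conclusion.** The point holds for non-serious bleeding. The trial looks for an antiplatelet effect in patients who may take aspirin, clopidogrel or both, yet bleeding is not prespecified, no visit asks about it, no scheduled exam follows a dose, and the listed safety tests include no blood count. Whether a reported minor bleed reaches the CRF depends on which of sections 8.4 and 8.5 is followed. Under-recording is therefore likely, by an amount the documents do not allow to be estimated; the table above only illustrates assumed values.

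The conclusion rests on two assumptions: that bleeding is the relevant clinical counterpart of reduced aggregation, and that unprompted patients leave some minor bleeding unmentioned. It does not affect the primary endpoint or the sample size. It is a low-cost improvement to safety information.

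**What to change.** 1. In section 6.4 and Table 1, add one fixed question on bleeding or bruising (yes/no, site, CTCAE v4.03 grade, the scale already named in section 8.3) at V2 and V5, with the same 8-week recall at both.
2. State that answers are recorded whatever their seriousness, and reconcile sections 8.4 and 8.5 accordingly.
3. If the question is also asked at V4 for safety, report those answers separately and keep them out of the between-period comparison. Note that being asked at V4 may prompt recall at V5.
4. In section 3.2, plan the number and percentage of patients with any bleeding in each 8-week period, with exact 95% limits. Label this descriptive only, because period is confounded with time in a single-arm fixed sequence.

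**Cost:** one CRF item at two existing visits (three if V4 is used), one descriptive table, and a wording change in sections 6.4, 8.4 and 8.5. The sample size and endpoints do not change. The downside is that a direct question will record more minor events than open questioning.
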